Data collected as part of the FDAC data collection tool will be the source of data for intervention cases. Ideally, data for the control group would be collected from the same data source, however Local Authorities do not systematically collect all the information collected by FDAC sites. Local Authorities will be asked to provide comparable data from their own case management systems and case notes based on a template developed by NatGen. As far as is possible, we will aim for comparable data collection. For example, we will collect data from fields used in statutory returns, such as those collected in the Children in Need census. Fields collected by control sites will be more limited relative to intervention sites. For

⁵ Although the CONSORT *Statement* was originally developed to guide the reporting of RCTs, many of its components also apply to other types of quasi-experimental impact studies. A flow diagram template will be downloaded from <http://www.consort-statement.org/>.

⁶

example, drug misuse will be based on data collected by Local Authorities, which may not be as accurate as the testing conducted in FDAC sites (e.g. drug testing using samples of parent's hair).

Our data collection template that will be completed by the Local Authorities will include detailed instructions and guidance for all key fields required to complete this evaluation. There will be cell validation in order to minimise blank cells and ensure data comparability across Local Authorities. We will only be able to use fields collected in both FDAC sites and Local Authorities in the matching.

Key characteristics that we intend to include in the matching are illustrated in Table 3. Each of these characteristics are collected in both the FDAC data collection tool and the control group data collection tool. These variables are important indicators of whether a case is suitable for FDAC (such as type of drug and alcohol misuse). However, it cannot account for subjective criteria that may be used by FDAC sites in determining which cases should be supported by FDAC. Table 3 also outlines how specific variables will be coarsened in matching.

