Local Authorities will be asked to complete this template using data from their own case management systems and case notes. Due to resourcing constraints faced by the Local Authorities, and following consultation, we removed some covariates from the planned analysis and data collection template. The original set of covariates can be found in Appendix C .

Table 3. Intended variables for matching intervention and control cases and coarsening strategy for child, parent and case-level outcomes			
Characteristics	Variable	Type	Coarsening Strategy
Child-level outcome: reunification			
Case characteristics	Date of issue	Date	Year and quarter
Parent characteristics	Primary carer – Age	Continuous	Age bands: Less than 18 years old, 18–24, 25–34, 35–44, 45 or older
	Primary carer – Gender	Categorical	No coarsening: Male, Female, Other, Unknown
	Primary carer – Ethnicity	Categorical	No coarsening: White, Asian/Asian British, Black African/Black Caribbean/Black British, Mixed/multiple ethnic groups, other, unknown
	Primary carer for how many children	Continuous	Bands: 0 (if not primary carer), 1, 2, 3 or more
	Primary carer – Age of youngest child cared for	Continuous	Age bands: Less than 12 months old, 1, 2–3, 4–7, 8–11, 12–16
	Primary carer – Past experience of domestic abuse	Categorical	No coarsening: Yes – perpetrator, Yes – Victim, Yes – both, No, Unknown
	Primary carer – Currently experiencing domestic abuse	Categorical	No coarsening: Yes – perpetrator, Yes – Victim, Yes – both, No, Unknown
	Primary carer – Whether misusing at time of referral	Categorical	No coarsening: Yes, No, Unknown

	Primary carer - Substance misuse type	Categorical	No coarsening: Drugs, Alcohol, Drugs and Alcohol, None, Unknown
Parent characteristics aggregated to case level	Number of parents in the case	Categorical	One, two three or more
Child characteristics	Age	Continuous	Age bands: Less than 12 months old, 1, 2-3, 4-7, 8-11, 12-16
	Gender	Categorical	No coarsening: Male, Female, Other, Unknown
	Ethnicity	Categorical	No coarsening: White, Asian/Asian British, Black African/Black Caribbean/Black British, Mixed/multiple ethnic groups, other, unknown
Parent-level outcome: substance misuse cessation			
Case characteristics	Date of issue	Date	Year and quarter
Parent characteristics	Age	Continuous	Age bands: Less than 18 years old, 18-24, 25-34, 35-44, 45 or older
	Gender	Categorical	No coarsening: Male, Female, Other, Unknown

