Primary carer for how many children	N/A	Number of children in household	We will derive a new parent-level variable from child-level data, counting how many children each parent cares for as primary carer, for both FDAC and non-FDAC groups.
Primary carer – Age of youngest child cared for	N/A	Age of youngest child in household	We will derive a new parent-level variable from child-level data, selecting the age of the youngest child the parent cares for as primary carer.
Number of children in the case	N/A	Number of children in household	We will derive a new case-level variable that is a count of the number of children in the case.
Age of youngest child in the case	N/A	Age of youngest child in household	We will derive a new case-level variable, calculated from the age variable in the child-level data.
Substance misuse type	Severity of parental alcohol misuse: High, Medium, Low, None, Unknown*	Substance misuse type: Drugs, Alcohol, Drugs and Alcohol, None, Unknown	FDAC data will be recoded to match non-FDAC data as follows: 1) If misusing at time of referral = No, we will code the substance misuse type as None; 2) If misusing at time of referral = Yes, we will check parental alcohol misuse and drug misuse and categorise their substance misuse type as Drugs, Alcohol, Drugs and Alcohol, or Unknown; 3) If misusing at time of referral = Unknown, we will recode the substance misuse type as Unknown
	Severity of parental drug misuse: High, Medium, Low, None, Unknown*		

*This is based on clinical judgements on substance misuse severity where guidance for the FDAC data collection tool is provided in Appendix D.

Minimum detectable effect size calculations

Power calculations were conducted in Stata 17.1 based on the anticipated matched sample size, using formulae from Dong and Maynard (2013). These formulae are presented in Appendix F. The results are presented in Table 5. The total number of non-FDAC cases will exceed the numbers prior to matching. Cases are then weighted so that there are equivalent FDAC and non-FDAC cases, so we assume equal sample sizes at analysis. Our assumptions are:

- Clustering of children within parents, with an ICC of 0.70
- No clustering of children within Local Authorities
- Variance explained by the uncoarsened covariates used in a regression model after matching, with an R-squared of 0.20 at level one and 0.10 at level two. We estimate this to provide a correlation of 0.45 and 0.32 respectively⁷

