The matching will be conducted using the user-written package *cem* in Stata 17.1 SE (Blackwell et al., 2010), which implements CEM as described in Iacus et al. (2009). The primary analysis will be conducted on an intention-to-treat basis where the outcome is non-missing. Where covariate data is missing, the *cem* package matches cases that are missing data on the same covariates. If missing outcome data exceeds five percent of the intervention sample, we will consider conducting a sensitivity analysis using multiple imputation (see missing data analysis).

Any intervention cases excluded from the analysis because no match can be found will be transparently reported using a CONSORT flow diagram. If more than five percent of intervention cases are lost because of issues with common support, we will consider adjusting how covariates are coarsened. This would involve collapsing categories of coarsened covariates and altering bin sizes. A summary of matching variables and how they will be coarsened can be found in Table 3.

Analysis

A “doubly robust” estimation of causal effects will be estimated for the matched sample, applying the weights assigned during the matching, including a binary indicator of allocation to FDAC, while also including the uncoarsened matching covariates in the regression model, following Funk et al. (2011). The “doubly robust” estimation reduces the risk that the average treatment effect on the treated (ATT) is biased, provided that either the matching (modelling exposure to the intervention) or the regression model (describing the relationship between the dependent and independent variables) is well specified (Funk et al., 2011). To account for the clustering of children within primary carers, cases and within sites (as shown in Table 1)⁸, we will use a multilevel logistic regression model. The full model is as follows:

$$P(\text{Reunification}_{ipcs}) = \text{logit}^{-1}(\beta_0 + \beta_1 \text{Intervention}_{ipcs} + \beta_2 X_{ipcs} + u_{pcs} + u_{cs} + u_s)$$

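### Blank covariates match only blanks while Unknown is a separate level, so an FDAC child with a blank field is likely to go unmatched because of coding alone

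*Supplement*

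**What the plan says.** All references are to version 2.0 of the study plan.

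- **Matching rule** (Analysis plan, Primary Analysis, Matching). Where covariate data are missing, the cem "package matches cases that are missing data on the same covariates". A blank is thus a value of its own.
- **Matching levels** (Table 3). Unknown is a listed level for several fields, for example "No coarsening: Yes, No, Unknown" for misuse at referral and "No coarsening: Drugs, Alcohol, Drugs and Alcohol, None, Unknown" for misuse type.
- **Data sources** (Data sources and availability). "Data collected as part of the FDAC data collection tool will be the source of data for intervention cases". Controls come from a template completed by Local Authorities, for which: "There will be cell validation in order to minimise blank cells and ensure data comparability across Local Authorities". The comparability named there is between Local Authorities, not between arms. No validation is described for the FDAC tool.
- **Harmonisation** (Table 4). FDAC severity fields have their own Unknown code ("Severity of parental alcohol misuse: High, Medium, Low, None, Unknown"). Where misuse status at referral is recorded as Unknown, "we will recode the substance misuse type as Unknown". No other field has a rule of this kind.
- **Remedy for lost cases** (Matching). "If more than five percent of intervention cases are lost because of issues with common support, we will consider adjusting how covariates are coarsened". The action described is to merge categories and change bins.
- **Interpretation** (Identification strategy). Intervention cases lost at matching are taken to show that no suitably similar control existed.

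**The concern.** A blank and a recorded Unknown can describe the same situation: nobody knows the value. Under the stated rule they fall in different strata. The control template is designed to keep blanks rare, so a control whose status is not known will tend to carry Unknown. If the corresponding FDAC field is left empty, the child needs a control with the same empty field, and few such controls should exist.

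At stake are FDAC children lost for a reason unrelated to comparability, with some precision and generalisability lost with them. The reported explanation would also be wrong, because the flow diagram would attribute the loss to missing common support. If the 5% trigger were reached, bins would be widened for everyone without merging blank and Unknown. The same Unknown levels recur in the parent-level and case-level lists of Table 3, so the secondary outcomes are exposed in the same way.

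**Working it through.** **Which fields are exposed.** Of the 14 child-level variables in Table 3, eight have an Unknown level: carer gender, ethnicity, past abuse, current abuse, misuse at referral and misuse type; child gender and ethnicity. Six have none: date of issue, carer age, number of children cared for, age of the youngest, number of parents and child age. Table 4 supplies a rule for misuse type, which leaves seven categorical fields without one. Table 4's recode gives rules for misuse at referral recorded as No, Yes or Unknown, but none for a blank.

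**Share of FDAC children at risk.** The documents give no blank rate, so p is assumed. With independent blanks over seven fields the share is 1 − (1 − p)^7:

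- p = 1%: 1 − 0.99^7 = 6.8%
- p = 2%: 1 − 0.98^7 = 13.2%
- p = 5%: 1 − 0.95^7 = 30.2%

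The share reaches 5% at p = 1 − 0.95^(1/7) = 0.7% per field. Five of the seven fields describe one carer, so blanks may cluster in the same records, which would lower these shares.

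**Chance that a child with one blank still matches.** Assume 600 controls, a fraction s of whom share the child's pattern on the other fields, and a control blank rate b in the field concerned. The chance is 1 − (1 − s × b)^600.

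- s = 1%: 0% at b = 0; 0.6% at b = 0.1%; 6% at b = 1%; 26% at b = 5%.
- s = 5%: 0%, 3%, 26% and 78% at the same values of b.
- A child with no blank and s = 1% matches with probability 1 − 0.99^600 = 99.8%.

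A match is therefore unlikely when control blanks are rare, but it is excluded only if there are none.

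**Reproducing the plan's detectable ratio.** Inputs from the section on minimum detectable effect size: 430 clusters, 600 children, ICC 0.70, R-squared 0.10 for parents and 0.20 for children, equal arms, two-sided 0.05, power 0.80, control rate 25%. With about 428 degrees of freedom the multiplier is about 2.81.

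- MDES = 2.81 × √(0.70 × 0.90/(0.25 × 430) + 0.30 × 0.80/(0.25 × 600)) = 0.2425
- OR = exp(0.2425 × π/√3) = 1.553
- RRR = 1.553/(0.75 + 0.25 × 1.553) = 1.364, or 9.1 points

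This agrees with the stated 1.36 and 9.1 points. It takes R-squared 0.10 on the parent term and the exponential form of the odds-ratio conversion. The figure assumes 300 matched FDAC children.

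**Effect of loss on precision.** Removing the same share of clusters and keeping equal weighted arms:

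| FDAC children lost | FDAC children left | Detectable ratio | Points |
|---|---|---|---|
| 0% | 300 | 1.364 | 9.1 |
| 5% | 285 | 1.374 | 9.4 |
| 10% | 270 | 1.386 | 9.6 |
| 20% | 240 | 1.411 | 10.3 |
| 30% | 210 | 1.443 | 11.1 |

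**Whether other provisions catch it.** Merging Table 3 levels joins listed levels to one another; blank is not a listed level. Imputation is triggered by missing outcomes, not missing covariates. The Missing data analysis section adds categories for missing covariates, but only in the drop-out model. The outcome model contains the uncoarsened covariates and has no stated missing category, so even a blank child who does match could be dropped there.

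**The case against.** The strongest reply is that nothing shows the FDAC tool leaves not-known fields blank. Table 3 gives one category list per variable for both arms. The FDAC tool has an Unknown code for at least the severity fields, and the earlier matching table in Appendix C already lists Unknown for ethnicity and both abuse fields. Silence about validation of that tool is not evidence of blanks. On the control side the aim is to minimise blanks, so some may remain. Losses will be shown in a flow diagram, and above 5% the coarsening will be reconsidered. All of this stands. It limits the claim to what the rule does to a blank if one occurs; the plan does expect missing covariates, since it has a rule for them.

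A reader might also infer bias: if incomplete FDAC records come from disengaged families, dropping them would raise the FDAC reunification rate. With 13.2% lost at a 20% rate, against 34.1% overall, the retained rate is (34.1 − 0.132 × 20)/0.868 = 36.2%, and 36.2/25 = 1.45. With no effect, and 15% in the lost against 25% overall, it is 26.5%, and 26.5/25 = 1.06. Both figures hold the control rate at 25%. The Identification strategy removes controls without an FDAC match and weights the rest to the FDAC strata, so the Unknown-coded counterparts are removed or down-weighted too. If they are removed and share the lost children's prospects, the no-effect case gives 26.5/26.5 = 1.00. In the other case the counterparts sit at 20/1.364 = 14.7%, the retained controls at (25 − 0.132 × 14.7)/0.868 = 26.6%, and the ratio is 36.2/26.6 = 1.36. If instead FDAC blanks mark disengagement and control Unknowns do not, the two codes are not equivalent and the direction cannot be derived from the documents.

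**Conclusion.** The point holds as a fault in the matching rule. Blank and Unknown are distinct strata, only the control template is described as validated against blanks, and codes are aligned to Unknown for one variable only. An FDAC child with a blank in one of the other seven categorical fields is likely, though not certain, to go unmatched. The plan's remedy would not by itself recover that child, and its interpretation would misname the cause.

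Under assumed independent blank rates of 1% to 2% per field, about 7% to 13% of FDAC children are at risk, fewer if blanks cluster. The consequence that can be shown is lost sample, precision and generalisability, with a 10% loss taking the detectable ratio from 1.36 to about 1.39. The documents do not support saying that such children will certainly be dropped, or that the estimated effect will be inflated. The change is still worth making: it replaces a stated rule with a better one at almost no cost.

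**What to change.** Replace the sentence on missing covariates in the Matching section with a rule along these lines: before matching at child, parent and case level, blank values of the categorical matching covariates in both arms are recoded to Unknown; matching uses the recoded values; and the same code enters the outcome model, so that these records are not dropped there.

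Report blank and Unknown counts by arm and by field. In the flow diagram, show matching losses due to missing data separately from losses due to lack of comparable controls. The recode does not reach the six child-level variables without an Unknown level, so the plan should also state how a blank in those is handled.

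The cost is one sentence, one recoding step and a small table. The downside is that a blank and a recorded Unknown are treated as equivalent; repeating the analysis without the recode checks how much that matters.

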2.0	1 Nov 2022	
 ● Added section about variations from original evaluation ● Updated number of FDAC sites and Local Authorities included in the study (Table 1) ● Updated Identification strategy section: changed severity of alcohol and drug misusing into type of misuse due to non-FDAC data availability ● Updated Outcome measure section: added an additional analysis of the number of different types of expert witness to deal with Research Question 5 ● Updated Matching section: updated Table 3 on matching variables; coarsening strategy for child, parent and case-level outcomes; and variables to be used by children-, parent- and case-level (details on changes can be tracked by comparing previous version of Table 3 “Intended variables for matching” in Appendix C) ● Updated Analysis plan section: changed model specification into a multilevel logistic regression to account for clustering effects; added a multilevel Poisson regression model to explore the difference between FDAC and non-FDAC cases in the number of different types of expert witness consulted during care proceedings. ● Updated Data source and availability section, in accordance with non-FDAC data availability ● Added new table listing misalignment between FDAC and non-FDAC data, along with derived variables to harmonise the data (Table 5) ● Updated Ethics & Participation section: regarding local authorities having to send out opt-out letters to parents receiving non-FDAC care proceeding ● Updated personnel list and timeline ● Expanded the date window for eligibility for study inclusion to maximise our sample size 
Minor changes:
 
 ● Used consistent terminology for child-, parent-, and case-levels of data ● Refer to the comparison group as non-FDAC care proceedings as usual, to match the language used with LAs ● Simplified the power analysis table to remove clusters with ICC = 0. (No change to calculation)

Table of contents

Table of contents	3
Background and Problem Statement	4
Children and Families Act 2014	4
The National Unit	4
Effectiveness	4
Variation between sites	5
Rationale for further evaluation of FDAC	5
Variations from original evaluation design	5
Intervention and Theory of Change	6
Impact Evaluation	8
Research questions	8
Participants	8
Design	9
Identification strategy	10
Data sources and availability	11
Minimum detectable effect size calculations	17
Outcome measures	18
Analysis plan	19

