FDAC is designed to be a 'problem solving' court that adopts a less adversarial approach than typical care-proceedings. It follows the principle of therapeutic jurisprudence, empowering families with a stronger voice in care proceedings.

How is the intervention delivered?

Each FDAC site has a dedicated FDAC judge. The FDAC judge has jurisdiction over both care-proceedings and the FDAC treatment intervention. The FDAC judge oversees fortnightly reviewing hearings with the multidisciplinary team. Lawyers do not attend the fortnightly review hearings. The multidisciplinary team provides treatment and support to parents, monitoring their progress and reporting back to the court at the fortnightly review hearings. These hearings aim to solve the problems faced by the parent through an open therapeutic forum.

The staffing of the multidisciplinary team varies across FDAC sites, though the core structure includes substance misuse specialists, social workers and an overall site manager.

When and where is the intervention delivered?

The intervention is delivered during care-proceedings, which typically last up to 26-weeks. In some circumstances, extensions to care-proceedings are granted.

There are fourteen FDAC sites, operating within Local Authorities. A full list of FDAC sites and the Local Authorities each site covers is detailed in Table 1, along with 12 Local Authorities who agreed to provide non-FDAC data as part of this evaluation.¹

Table 1 FDAC sites and Local Authorities	
FDAC site	Local Authority
Pan-Bedfordshire	Central Bedfordshire*
	Luton
	Bedford
Birmingham and Solihull	Birmingham City*
	Solihull*
Coventry	Coventry*
	Warwickshire*
East Sussex	East Sussex
Gloucestershire	Gloucestershire
Kent	Kent*
Leeds	Leeds City Council*
London	Bromley
	Camden
	Croydon
	Kingston
	Lambeth
	Merton
	Redbridge*
	Richmond
	Sutton
	Wandsworth
Milton Keynes and Buckinghamshire	Milton Keynes
	Buckinghamshire
Newcastle, Gateshead & North Tyneside	Newcastle
	Gateshead
	North Tyneside
Somerset	Somerset
Southampton	Southampton City Council*

¹ Only one Local Authority who does not operate an FDAC site agreed to provide data.

Stockport	Stockport*
Walsall, Sandwell and Dudley	Sandwell
	Dudley
	Walsall*
Not operating FDAC site	Manchester*

* indicates the 12 Local Authorities that have agreed to provide data as part of this evaluation.

Variation and iterations

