Appendix F – Power calculation formulae

The formula used to estimate the power of the primary analysis are adapted from Dong and Maynard (2013). The MDES is calculated as follows:

$$MDES = M_{K(J-2)-g_2} \sqrt{\frac{\rho(1-R_1^2)}{P(1-P)JK} + \frac{(1-\rho)(1-R_2^2)}{P(1-P)JKn}}$$

Where:

- ρ is the intracluster correlation;
- R_1^2 and R_2^2 is the variance explained at level one and level two respectively;
- n is the average number of children per family
- J is the average number of parents per Local Authority
- K is the number of Local Authorities

The multiplier, $M_{K(J-2)-g_2}$ is calculated as follows:

$$M_{K(J-2)-g_2} = T_1 + T_2$$

Where T_1 (precision) and T_2 (power) are drawn from the inverse students' t-distribution as:

$$T_1 = \alpha, K(J - 2) - g_2$$

$$T_2 = 2\beta, K(J - 2) - g_2$$

Where g_2 is the number of covariates at level two, alpha is the type one error rate and beta is the type two error rate. We then convert the MDES to an odds ratio:

$$OR = (MDES * \frac{\pi}{\sqrt{3}})^e$$

The relative risk ratio is then estimate using the prevalence of the outcome in control, $Prev_c$:

$$RRR = \frac{OR}{(1 - Prev_c) + (Prev_c * OR)}$$

Trial Evaluation Protocol
Family Drug and Alcohol Courts
Evaluator: NatCen Social Research
Principal investigator: [name]

Evaluation of Family Drug and Alcohol Courts

Intervention Developer	Family Drug and Alcohol Courts in England
Delivery Organisations	Family Drug and Alcohol Courts in England
Evaluator	NatCen Social Research
Principal Investigator	[name]
Protocol Author(s)	[name], [name], [name], [name]
Type of Trial	Quasi-experimental design: Coarsened Exact Matching
Age or Status of Participants	Parents in care proceedings; Children of Parents in care proceedings
Number of Participating Local Authorities	31
Number of Children and Families	600 children (300 intervention; 300 control): 430 families (215 intervention; 215 control)
Primary Outcome(s)	Reunification
Secondary Outcome(s)	Parental alcohol and drug misuse cessation, number of contested hearings, use of expert witnesses, parent-child relationship, parental mental health.
Contextual Factors	Covid-19

Table of contents

Table of contents	2
Background and Problem Statement	3
Intervention and Theory of Change	4
Impact Evaluation	6
Implementation and process evaluation	20
Cost evaluation	23
Ethics & Participation	24
Registration	24
Personnel	25
Timeline	25
References	27

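### The 80% power for a relative risk of 1.36 assumes no area clustering, yet six of the 15 site codes hold one arm only and the primary model allows for site clustering; power is then somewhat below 80%

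*Supplement*

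**What the plan says.** The section on minimum detectable effect size calculations lists "Clustering of children within parents, with an ICC of 0.70", then "No clustering of children within Local Authorities", and covariates "with an R-squared of 0.20 at level one and 0.10 at level two". On allocation it says "so we assume equal sample sizes at analysis". With 25% reunification in control, 300 + 300 children and 215 + 215 cases, it states 80% power for a relative risk of 1.36, or 9.1 percentage points.

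Appendix F gives the formula. It has no area variance term, and its degrees of freedom are K(J-2) less the number of level-two covariates. K is the number of Local Authorities and "J is the average number of parents per Local Authority". Removing two means per Local Authority describes a layout with both arms in every area.

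In Table 1 of version 2.0 an asterisk "indicates the 12 Local Authorities that have agreed to provide data as part of this evaluation". The Analysis section replaces the regression with a multilevel logistic model "To account for the clustering of children within primary carers, cases and within sites", with a random intercept at each level. The footnote on sites gives Manchester its own code. On power, the version history says "Simplified the power analysis table to remove clusters with ICC = 0. (No change to calculation".

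**The concern.** The power section sets area variance to zero, while the analysis section treats site variance as something to be modelled. The value of that variance matters little if both arms are present in the same proportion in every site, because site effects then cancel out of the comparison. Table 1 does not give that layout. Where a site holds one arm only, or very unequal shares of the two, part of the treatment comparison is made between sites, and site variance enters the standard error.

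At stake is the stated precision of the primary outcome. Table 5 is the protocol's only power statement, and the remark on power for secondary outcomes is argued from it. A reader facing a null result on reunification would rely on it. The point holds even if site effects are unrelated to treatment.

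**Working it through.** **Step 1: reproduce the plan's figure.** Inputs from the power section: ICC 0.70, R-squared 0.20 (child) and 0.10 (parent), 1.4 children per case, 430 cases, equal allocation, two-sided alpha 0.05, power 0.80, control rate 25%.

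- Variance per family: v = 0.70 × 0.90 + 0.30 × 0.80 / 1.4 = 0.630 + 0.171 = 0.801.
- Detectable difference: 2.80 × √(0.801 / (0.25 × 430)) = 0.242 SD.
- Odds ratio: exp(0.242 × π/√3) = 1.551.
- Relative risk: 1.551 / (0.75 + 0.25 × 1.551) = 1.363, or 9.1 points.

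This matches the stated 1.36. It uses the standard forms: Appendix F prints the two R-squared terms in swapped places, and its odds ratio expression as printed does not give 1.36.

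**Step 2: the Table 1 layout.** Sites in Table 1 order, Manchester last:

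- Local Authorities served: 3, 2, 2, 1, 1, 1, 1, 10, 2, 3, 1, 1, 1, 3, 0 (total 32).
- Local Authorities supplying controls: 1, 2, 2, 0, 0, 1, 1, 1, 0, 0, 0, 1, 1, 1, 1 (total 12).

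Nine codes hold both arms. Five are FDAC only (East Sussex, Gloucestershire, Milton Keynes and Buckinghamshire, the Newcastle group, Somerset) and one is control only.

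The documents give no case counts by site, so two spreads of the 215 FDAC families are assumed; the 215 controls are spread equally over the 12 Local Authorities.

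- Equal by site: 215/14 = 15.4 FDAC families per site, so 5 × 15.4, about 77 (36%), are in FDAC-only sites.
- Proportional to Local Authorities: 215 × 8/32 = 53.8 (25%) are in FDAC-only sites. London has 215 × 10/32 = 67.2 FDAC families against 215/12 = 17.9 controls.

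**Step 3: add a site intercept.** For a site with m families, f of them FDAC, site variance τ and design matrix X (constant, FDAC indicator), the information is X'X/v − [τ/(1 + τm/v)] ww', with w = (m, f)/v. Sum over the 15 codes and invert to get the variance of the treatment effect. Let R be its ratio to the Appendix F variance. Power at 0.242 SD is Φ(2.80/√R − 1.96). For example, R = 1.075 gives Φ(2.70 − 1.96) = 77.1%.

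Two conventions for τ are shown. With total variance fixed, v becomes 0.801(1 − τ). With site variance added, v stays at 0.801.

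| Convention | FDAC spread | R at τ = 0.02 / 0.05 / 0.10 | Power | Detectable RR |
|---|---|---|---|---|
| Fixed total | Equal by site | 1.075 / 1.114 / 1.112 | 77.1 / 75.6 / 75.7% | 1.378 / 1.385 / 1.385 |
| Fixed total | Proportional | 1.132 / 1.188 / 1.196 | 75.0 / 72.9 / 72.6% | 1.388 / 1.399 / 1.400 |
| Added | Equal by site | 1.096 / 1.168 / 1.227 | 76.3 / 73.6 / 71.5% | 1.382 / 1.395 / 1.406 |
| Added | Proportional | 1.153 / 1.245 / 1.318 | 74.2 / 70.9 / 68.4% | 1.392 / 1.409 / 1.422 |

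These are powers at the unrounded 1.363. At 1.36 each is just over half a point lower (79.4% at τ = 0).

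**Step 4: checks.** With both arms balanced in all 14 sites and variance added, power does not change at any τ tried (0.05 to 0.20), so the loss comes from the layout. With very large τ in the added convention, power under the Table 1 layout levels off at about 67% (equal) and 63% (proportional).

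**The case against.** The zero is a declared assumption, the arithmetic follows from it, and the site ICC and caseload spread used here are mine. That stands: this is a dispute about an input, and the size of the loss can only be given as a range. But zero has no stated justification, and it conflicts with the plan's own model.

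The loss is small at small values. At τ = 0.01, added, power is still 78% (equal) or 76% (proportional).

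The number of families may differ from 215 per arm. The caseload estimate refers to January 2021 to June 2022, while eligibility now starts in October 2019; fewer Local Authorities take part. Net power could move either way. That supports redoing the calculation with actual counts.

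The practical consequence is limited. Version 2.0 is dated 1 November 2022, after the last eligible final hearing in October 2022, and the primary model carries the site intercept whatever Table 5 says. The estimate and its interval do not depend on Table 5.

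Two stronger readings are tempting. A reader might infer that the zero assumption was harmless in version 1.0 and that the redesign alone broke it. The documents do not settle this, because it depends on how cases were spread. On the 31-authority layout with FDAC families equal by site and controls equal by Local Authority, power is already 77.2 / 76.1 / 75.5% at added site variance 0.02 / 0.05 / 0.10; it stays at 80% only if FDAC families are also proportional to Local Authorities. A reader might also infer a collapse of power, as when the arms sit in entirely separate sites (about 49% at 0.05). Nine two-arm sites rule that out.

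**Conclusion.** The concern holds, at modest size. The stated 80% power for a relative risk of 1.36 rests on zero site variance, in a layout where site variance does not fully cancel and under a model that allows for it. For site ICCs of 0.02 to 0.10 as a share of fixed total variance, power is about 73-77% and the detectable relative risk about 1.38-1.40. The lower figures, down to 68% and 1.42, arise only if site variance is added on top of the plan's variance.

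These results assume 215 families per arm, the two caseload spreads shown, and the plan's own effect-size metric. They ignore unequal matching weights and the small number of sites, which would usually lower power further. The direction is the same in every scenario in the table; the exact figure needs counts by site.

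**What to change.** Recalculate power on the Table 1 layout with the primary model's site intercept, using actual FDAC and control counts by site where known and labelled assumptions where not. Restate Table 5 as a range over stated site ICCs, for example 0.02 to 0.10, and say whether the ICC is a share of fixed total variance or is added to it. Replace the no-clustering bullet accordingly, and note that the figure is no longer unchanged from version 1.0.

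The cost is one recalculation and a less favourable stated power. It needs no new cases, data or change to the analysis model.
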